**Tool Revision History:**

Version Number	Version Date	Summary of Revisions Made
1.0	April 3, 2022	Original Version (initial submission to IRB)
2.0	February 8, 2023	modified version

**Statement of Compliance**

This study will be conducted in accordance with the Code of Federal Regulations on the Protection of Human Subjects (45 CFR Part 46), 21 CFR Parts 50, 56, 312, and 812 as applicable, any other applicable US government research regulations, and institutional research policies and procedures. The International Conference on Harmonisation (“ICH”) Guideline for Good Clinical Practice (“GCP”) (sometimes referred to as “ICH-GCP” or “E6”) will be applied only to the extent that it is compatible with FDA and DHHS regulations. The Principal Investigator will assure that no deviation from, or changes to the protocol will take place without prior agreement from the sponsor and documented approval from the Institutional Review Board (IRB), except where necessary to eliminate an immediate hazard(s) to the trial participants. All personnel involved in the conduct of this study have completed Human Subjects Protection Training.

**List of Abbreviations**

AE	Adverse Event/Adverse Experience
CFR	Code of Federal Regulations
CRF	Case Report Form
CSOC	Clinical Study Oversight Committee
DCC	Data Coordinating Center
DHHS	Department of Health and Human Services
DSMB	Data and Safety Monitoring Board
FFR	Federal Financial Report
FWA	Federalwide Assurance
GCP	Good Clinical Practice
HIPAA	Health Insurance Portability and Accountability Act
HI	HemoPill Index
ICF	Informed Consent Form
ICH	International Conference on Harmonisation
IRB	Institutional Review Board
ISM	Independent Safety Monitor
MOP	Manual of Procedures
N	Number (typically refers to participants)
NIH	National Institutes of Health
OHRP	Office for Human Research Protections
OHSR	Office of Human Subjects Research
PI	Principal Investigator
QA	Quality Assurance
QC	Quality Control
SAE	Serious Adverse Event/Serious Adverse Experience
SOP	Standard Operating Procedure
UGIB	Upper Gastrointestinal Bleeding
US	United States

[figure not shown]
**Protocol Summary**

Title	Presence or Absence of blood in the GI lumen – Relation between a HemoPill acute measurement with a subsequent endoscopic finding
Short Title	PROOF (Presence or Absence of blood in the GI lumen – Relation between a HemoPill acute measurement with a subsequent endoscopic finding)
Brief Summary	Patients scheduled for endoscopy on the basis of suspected UGIB are generally eligible for inclusion into the trial. After patient screening, information and obtaining informed consent, a patient is enrolled into the trial. Shortly before the scheduled endoscopy is performed, the patient ingests a HemoPill acute. Endoscopy is performed as scheduled. Blood within the GI lumen is identified if present and pictures are taken. Pathologies, if found, are treated as per clinical standard. The HemoPill acute measurement regarding presence or absence of blood in the GI lumen is compared to observations made during endoscopy. For statistical validity, 43 patients are required. Considering dropouts, a recruitment goal of 50 patients is defined.
Phase	N.A.
Objectives	The objective of the study is to determine the clinical relation between the detection of blood in the GI lumen using the HemoPill acute (trial procedure) with the detection of bleeding / a bleeding source during an endoscopic examination (control procedure).
Methodology	Intraindividual comparison of HemoPill acute measurement to endoscopic work up.

Endpoint	
Effectiveness Endpoints:
 
 
- Technical effectiveness endpoint
 
 
Technical success, defined as:
 
Successful data transmission of the HemoPill acute to the HemoPill Receiver
 
 
- Clinical effectiveness endpoint
 
 
Result accuracy: Clinical relation between HemoPill acute measurement (trial procedure) and endoscopic findings (control procedure) according to defined events for true positive, true negative, false positive, false negative.
 
Safety Endpoints:
 
 
- Adverse events / complications associated with trial or control procedure, such as:
 
 
Trial procedure:
 
 
○ Aspiration of the capsule on ingestion
 
○ Delayed excretion, or failure to excrete the capsule (capsule retention)
 
○ Obstruction of the digestive tract
 
○ Injury to tissue structures during the passage of the HemoPill acute through the digestive tract. In particular, this may involve: 
 
■ Injury to the mucosa
 
■ Bleeding, e.g., variceal bleeding
 
■ Perforations
 
 
 
 
Control procedure:
 
 
○ Cardiopulmonary adverse events
 
○ Infection
 
○ Perforation
 
○ Bleeding (iatrogenic)
 

Study Duration	March 18, 2022 to July 31 st , 2022
Participant Duration	Single visit, patient participation ends with conclusion of endoscopy
Population	Adult subjects (meeting inclusion criteria) with suspected UGIB due to clinical and / or laboratory findings and therefore scheduled for endoscopy
Study Sites	NYU Langone Health [name]
Number of participants	Recruitment goal: 50 Patients; Statistical validity reached at 43 Patients w/o dropouts.

Description of Agent/Procedure	
HemoPill acute:  A capsule equipped with a photometric sensor for the detection of blood or hematin in the gastrointestinal tract. The capsule can be ingested and travels through the gastrointestinal tract naturally. For approximately 9 hours, the photometric sensor measures the absorption of light at specific wavelengths through the contents of the gastrointestinal lumen. Blood and hematin have a specific absorption behavior for the defined wavelengths used. The HemoPill acute capsule makes a measurement every 12 seconds and wirelessly transmits data to the HemoPill Receiver that displays the HemoPill acute data.
 
HemoPill Receiver:  Handheld device that displays HemoPill acute data. The HemoPill Receiver displays the data in a graphical form as well as the current value and the highest measured value. The threshold value for confirmation of presence of blood or hematin is displayed for reference.
		
Reference Therapy	Endoscopy		
Key Procedures	
Diagnostic procedures used leading to a suspicion of UGIB are not within the scope of this trial as these procedures are necessary irrespective of trial participation. A suspicion of UGIB, however justified, is a prerequisite for trial participation.
 
Endoscopy and associated procedural steps are omitted as endoscopy is scheduled for trial participants irrespective of trial participation.
		
Statistical Analysis	
Provide patient information and obtain informed consent. Screen by inclusion and exclusion criteria, document.
 
Activation of the HemoPill acute by the investigator as per instructions for use.
 
Ingestion of HemoPill acute capsule by the trial participant with a minimal amount of water.
 
Data collection on the HemoPill Receiver from ingestion of the HemoPill acute capsule until conclusion of endoscopy.
		
	
Relation between HemoPill acute measurements and endoscopic findings along the lines of the following definitions for “true positive”, “true negative”, “false positive”, “false negative”:
 
 
 True Positive	HemoPill acute measurement indicates presence of blood; Endoscopy identifies fresh blood or hematin in the GI lumen.	
 
	True Positive	HemoPill acute measurement indicates presence of blood; Endoscopy identifies fresh blood or hematin in the GI lumen.
True Positive	HemoPill acute measurement indicates presence of blood; Endoscopy identifies fresh blood or hematin in the GI lumen.		

	True Negative	HemoPill acute measurement does not indicate presence of blood; Endoscopy does not identify fresh blood or hematin in the GI lumen in quantities > 20 mL; Minimum latency of 20 minutes achieved.
	False Positive	HemoPill acute measurement indicates presence of blood; Endoscopy does not identify fresh blood or hematin in the GI lumen.
	False Negative	HemoPill acute measurement does not indicate presence of blood in the GI lumen; Endoscopy identifies fresh blood or hematin in the GI lumen in quantities > 20 mL; Minimum latency of 20 minutes achieved.

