The resulting decimal values are rounded down to have one decimal number (e.g.  $0.88 = 0.8$ ,  $1.31 = 1.3$ ). by rounding down, the HI-value has the same clinical significance as the quotient (e.g. a quotient of  $Q = 99$  corresponds to a HI-value of  $HI = 0.9$ , therefore both are not crossing 100 and 1.0, respectively).

If the measuring gap is filled with blood, violet light can be almost completely blocked, while red light passes through the sensor gap almost entirely unimpeded. In this case, the HI-value can reach its maximum of 1.5.

Other foodstuffs can return a HI-value of up to 0.7 in individual cases. In empty stomachs the sensor can come into contact with undiluted bile as it passes through the stomach passage. This can lead to a HI-value of approx. 1.0. Several substances have been tested in an animal study, see Volume 005.

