### 2.1.3 Clinical application

For intended examination, the detection of blood in the upper gastrointestinal tract, the patient swallows the HemoPill acute capsule (after activation) ((1) in Figure 2-9). The capsule must be taken with at least 100 ml water, which aids swallowing and promotes the suspension of blood. The HemoPill acute continuously sends measurement data which are received and recorded by the HemoPill Receiver ((2) in Figure 2-9). Measurement data are displayed on the HemoPill Receiver for interpretation by the user ((3) in Figure 2-9). After the data acquisition procedure, the data can be printed using the HemoPill Printer.

[figure not shown]

Figure 9: Operation principle of the HemoPill acute system

The HemoPill acute continuously send approx. 5 measured values per minute to the HemoPill Receiver. The duration of the measurement is approx. 9 hours from activation of the HemoPill acute. The values measured by the capsule are displayed numerically and as a curve diagram on the display of the HemoPill Receiver (Figure 2-10). Furthermore, the capsule ID, which is individual for each individual capsule, is shown on the display, ensuring an allocation to the patient. The capsule ID is indicated directly on the blister packaging of the capsule. The separately enclosed patient labels (four stickers) serve the document in the patient file and do also include the capsule ID.

The numerical display shows the maximum HI value ( $^{MAX}HI$ ) (see (1) in Figure 2-10) and the last measured value ( $^{LAST}HI$ ) (see (2) in Figure 2-10)). The respective measuring time is located below.  $^{LAST}HI$  is updated with each measured value received (about 5 times per minute).  $^{MAX}HI$  updates every minute during the first hour, after the first hour until the 9th hour about every 8 minutes. The  $^{MAX}HI$  value is also plotted as a curve over time (Figure 2-10). By pressing the information button (see (3) in Figure 2-10) information on interpreting the HI values are shown.

[figure not shown]

Figure 10: Information on the display of the HemoPill Receiver

For interpretation of the HI values the following procedure is recommended:

1. First, interpret the maximum HI value within 10 minutes from swallowing the HemoPill acute, see Table 3.
2. Then interpret, independently of this, the maximum HI value in the further course of the measurement ( $\geq 10$  minutes after swallowing), see Table 4.

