## 4 Study Design and Endpoints

### 4.1 Description of Study Design

Patients are included according to the defined inclusion criteria and prepared for endoscopy. At the latest possible time before endoscopy, a HemoPill acute capsule is administered with a minimal amount of water. The HemoPill receiver is stored in a carrying bag. The transparent part of the bag over the display of the receiver is covered with tape. The LED light is left uncovered, so a successful signal transmission can be checked at any times. The investigator is unaware of the HemoPill acute measurement result until endoscopy has concluded. After a latency of minimum 20 minutes, maximum 60 minutes, endoscopy is performed as scheduled, identifying blood within the GI lumen, if present. A minimum latency is introduced to ensure HemoPill acute is able to make a measurement without interference from endoscopy, e.g., insufflation or endoscopic light.

The amount of blood identified in endoscopy is visually analyzed and pictures are taken. For the estimation of the amount of blood present in a patient, comparative images are provided. Assessment categories are:  $x < 20$  mL and  $x > 20$  mL. The detection threshold is introduced to provide a point of reference for the HemoPill acute detection rate.

Pathologies, if found, are treated as per clinical standard. HemoPill acute measurements regarding presence or absence of blood are put in relation to endoscopic findings.

Endoscopic images are further analyzed to determine the digestive state of the blood found as HemoPill acute is capable of detecting fresh blood or hematin. Blood digested to a point beyond hematin is no indicator for an acute bleeding pathology. The following foreseeable combination of events are described and allocated to “True Positive”, “False Positive”, “True Negative”, and “False Negative”.

- **True positive:**  
HemoPill acute measurement indicates presence of blood; Endoscopy identifies fresh blood or hematin in the GI lumen
- **False positive:**  
HemoPill acute measurement indicates presence of blood; Endoscopy does not identify fresh blood or hematin in the GI lumen.
- **True negative:**  
HemoPill acute measurement does not indicate presence of blood; Endoscopy does not identify fresh blood or hematin in the GI lumen in quantities  $> 20$  mL; Minimum latency of 20 minutes achieved.
- **False negative:**  

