**6.1.9 Duration of Therapy**

From HemoPill acute capsule ingestion to start of endoscopy, a maximum of 60 minutes elapse. Duration of endoscopy depends on presence or absence of pathologies and time needed for treating pathologies if found.

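### The maximum HI that classifies a patient is not limited to readings before scope insertion, so a reading made during endoscopy can set the result of a test meant to precede it

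*Combined protocol and SAP*

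**What the plan says.** **Recording window.** The procedural steps in the Protocol Summary specify "Data collection on the HemoPill Receiver from ingestion of the HemoPill acute capsule until conclusion of endoscopy". Recording therefore has an end, but that end lies after the reference procedure.

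**Classification rule.** Section 2.1.3 reads the HI in two stages. The first is the maximum within 10 minutes of swallowing, positive from 0.8 (Table 3). For the second it says "Then interpret, independently of this, the maximum HI value in the further course of the measurement", positive from 1.0 (Table 4). The second stage has no upper time limit.

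**When the result is read.** Section 4.1 has the receiver display taped over and states "The investigator is unaware of the HemoPill acute measurement result until endoscopy has concluded".

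**What the analysis section adds.** Section 10.4.2 says the investigator turns the HI into positive or negative and refers to 2.1.2.2 for detail. That section gives the HI formula, the rounding and some interfering substances. It gives no decision table and no time window. Section 6.1.4 refers to the instructions for use, which are a separate document.

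**What the design intends.** The title speaks of "Relation between a HemoPill acute measurement with a subsequent endoscopic finding". Section 10.4.1 says the index test is done first in every participant. Section 4.1 explains the 20-minute minimum: "A minimum latency is introduced to ensure HemoPill acute is able to make a measurement without interference from endoscopy, e.g., insufflation or endoscopic light".

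**The concern.** In an accuracy study the index result should be fixed before the reference procedure can affect it. Here the recording window, the open-ended maximum and the late reading together allow values obtained with the endoscope in place to decide the capsule result.

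A maximum can only rise as readings are added, so late readings can turn negatives into positives and never the reverse. The plan itself names two ways in which endoscopy could matter: iatrogenic bleeding, listed among the control-procedure complications in 4.2.2, and the interference from insufflation or endoscopic light in 4.1. For insufflation and light the documents do not say which way the HI would move.

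At stake are the sensitivity, specificity and accuracy that section 2.4.1 describes as the purpose of the trial. They are meant to describe a capsule read before endoscopy, not one read partly during it.

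**Working it through.** **1. Do the texts close the window?** The 20-minute latency in 4.1, repeated in the true-negative definition ("Endoscopy does not identify fresh blood or hematin in the GI lumen in quantities > 20 mL; Minimum latency of 20 minutes achieved") and in the false-negative definition, guarantees that some readings precede the scope. It does not exclude later ones. No section limits the classifying maximum to the period before insertion. By contrast, the earlier feasibility trial in 2.2.5 compared endoscopy with capsule data from the first 10 minutes after ingestion.

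**2. The plan's own sample size.** Accuracy of 50% against 75% gives w = sqrt(2 × 0.25² / 0.5) = 0.50. A chi-square test with 1 degree of freedom, alpha 0.05 and power 0.90 then needs n = 43, as stated. (The stated w = 0.62 would give 28 with 1 degree of freedom. That is a separate matter and does not affect this point.)

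**3. Expected table at n = 43.** Section 2.1 gives the planning study's counts among 60 patients: 20 true positives, 15 false positives, 25 true negatives, no false negatives. Accuracy is 45/60 = 75% and specificity 25/40 = 62.5%, matching section 10.5. Scaled by 43/60:

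- with blood: 14.33
- without blood: 28.67, of which true negatives 17.92 and false positives 10.75
- correct: 32.25

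**4. Effect of one flip, by type of patient.**

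- *No blood (true negative to false positive).* Accuracy falls by 100/43 = 2.3 points and specificity by 100/28.67 = 3.5 points. Using only the planning study's endoscopically checked patients (20 TP, 11 FP, 20 TN, N = 51), the blood-free number is 43 × 31/51 = 26.14 and the loss 100/26.14 = 3.8 points.
- *Blood under 20 mL (true negative to true positive under the 4.1 definitions).* Accuracy is unchanged. Specificity becomes (17.92 − 1)/(28.67 − 1) = 61.1%, a fall of about 1.4 points. Iatrogenic blood recorded as an endoscopic finding would act in the same way.
- *Missed blood over 20 mL (false negative to true positive).* Accuracy rises by 2.3 points and sensitivity by 100/14.33 = 7.0 points. The planning sensitivity of 100% implies no such patients. If pre-endoscopy sensitivity were 80% (an assumption) and half the misses crossed the threshold during endoscopy, reported sensitivity would be 0.80 + 0.20 × 0.5 = 90%.

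**5. Effect on the primary test.** Chi-square for accuracy against 50% at n = 43 (expected 21.5 per cell):

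- 28 correct: 2 × 6.5²/21.5 = 3.93, p = 0.047
- 27 correct: 2 × 5.5²/21.5 = 2.81, p = 0.093

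From about 32 correct, five blood-free flips (32 − 5 = 27) lose significance, which is 5/17.9 = 28% of the expected true negatives. With an exact two-sided binomial test, 29 correct gives p = 0.032 and 28 gives p = 0.066, so four flips suffice (22%).

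**6. Illustration under assumed flip rates.** The documents give none. If 5%, 10% or 20% of true negatives were blood-free and crossed only during endoscopy:

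| Assumed rate | Accuracy | Specificity | Exact power |
|---|---|---|---|
| 0% | 75.0% | 62.5% | 0.90 |
| 5% | 72.9% | 59.4% | 0.84 |
| 10% | 70.8% | 56.2% | 0.75 |
| 20% | 66.7% | 50.0% | 0.53 |

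**The case against.** The best defence is that the intent is plain. The title, section 10.4.1 and the stated reason for the latency all describe a pre-endoscopy measurement, and the guidance in 2.1.3 is general device guidance for a recording of about nine hours. The instructions for use may also limit the window, which cannot be checked here. This makes the point a drafting gap rather than a deliberate choice. It does not remove it: the one printed rule, applied to the data the plan collects and read when the plan says, includes readings made during endoscopy.

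The gap may also be repairable afterwards. The receiver saves values (2.1.1.1), and 10.4.9.1 plans a listing with measurement results and time points. That stands, but a cut-off chosen after the results are known is weaker than one written in advance.

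A reader might infer more than the documents support, in four ways:

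- *Longer endoscopy biases the comparison.* Section 6.1.9 says "Duration of endoscopy depends on presence or absence of pathologies and time needed for treating pathologies if found", so patients with treated lesions are recorded for longer. To the extent that they also have blood, the planning sensitivity of 100% already makes them capsule-positive, and nothing is left to flip. Only blood-free patients with a treated lesion, or those with under 20 mL, fit the argument, and no number is given for them.
- *Bile during endoscopy creates false positives.* Section 2.1.2.2 describes "undiluted bile as it passes through the stomach passage. This can lead to a HI-value of approx. 1.0", which is the later threshold. But bile is not caused by endoscopy and can act equally in the 20 to 60 minutes before it. Ending the window at insertion does not remove that.
- *More readings mean proportionally more risk.* At five readings per minute, each 10 minutes of endoscopy adds 50. Readings 12 seconds apart on the same contents are not independent chances, so the count does not measure added risk.
- *The bias favours the device, or defeats it.* Blood-free flips lower specificity, while flips in missed bleeds raise sensitivity. The net direction is unknown.

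**Conclusion.** The point holds as a minor one. As written, readings made during the reference procedure can set the index result, against the design's own aim. The documents give neither a flip rate nor an endoscopy duration, so the size can be stated only per flip: for a blood-free patient, about 2.3 points of accuracy and 3.5 points of specificity at n = 43, assuming the planning study's table carries over.

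The documents do not support reading this as a threat that overturns the primary test. Starting from the expected 32 correct, about five blood-free flips are needed (four with an exact test). A trial that landed nearer the boundary would have less margin, as the assumed power figures show. The main exposure is in the specificity and sensitivity estimates.

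**What to change.** In 10.4.2, state the rule in full, for example:

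*The capsule result is based on the maximum HI from ingestion to the recorded time of scope insertion. It is positive if the maximum is at least 0.8 within 10 minutes of swallowing or at least 1.0 after that, and negative otherwise. Readings after insertion are listed separately and do not enter the 2 x 2 table.*

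Replace the reference to 2.1.2.2 with 2.1.3, Tables 3 and 4. If the longer window is in fact wanted, say so in advance and give the reason.

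**Cost.** Wording, plus recording the insertion time, which the 20 to 60 minute latency already requires. Between 20 × 5 = 100 and 60 × 5 = 300 readings per patient remain, and 43 evaluable of 50 enrolled is unchanged. The displayed maximum updates every minute in the first hour and about every 8 minutes after that (2.1.3), so for scopes starting near 60 minutes use the saved single values where available.

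**Downside.** Positives that first appear during endoscopy no longer count.

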#### **2.1.1 Study importance**

As described in the above-mentioned publications, further tools for risk stratification in patients with suspected UGIB are in demand to identify high risk patients and adequately allocate resources. The clinical data on the use of the HemoPill in Europe is generally positive and promising. As Brunk T et al. conclude, thus far no HemoPill negative patient developed a clinically significant GI bleeding until discharge and every endoscopically confirmed bleeding pathology was associated with a previously positive HemoPill measurement. The proposed study further investigates the safety and performance profile of the HemoPill by controlling and limiting latency to endoscopy. HemoPill may prove to be a valuable tool for the US healthcare system by reliably providing information on the presence or absence of blood in the GI tract. HemoPill does not require patient preparation and measurement data is displayed in a way that allows for immediate, real-time interpretation. Thus far, HemoPill has a high technical success rate and is well tolerated by patients. Only patients who are already scheduled for endoscopy for suspected UGIB are eligible for participation in the study and endoscopy is neither delayed nor prolonged by the study protocol. The potential benefits for the US healthcare system are already highlighted in publications describing the use of the subject device in Europe.

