#### 6.3.1 Administration of Procedural Intervention

The investigator activates the HemoPill acute capsule by using the HemoPill Receiver. A data connection to the HemoPill Receiver is established. The activated HemoPill acute, still within the blister, is handed to the trial participant for ingestion with a minimal amount of water. Ingestion is timed under consideration of the previously established scheduling for endoscopy. Between HemoPill acute ingestion and start of

endoscopy, a minimum of 20 minutes should have elapsed. No more than 60 minutes between HemoPill acute ingestion and start of endoscopy should elapse. A trial participant is subjected to one intervention.

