### 10.3 Analysis Datasets

All patients with full study protocol participation are included in the analysis dataset, i.e. with results on both measurements, the subjective device (HemoPill acute capsule) and the control product (endoscopy). Therefore, only patient withdrawal or termination by the investigator can lead to exclusion from the analysis dataset (described in detail in section 5.7).

No further (sub-)analysis datasets are planned.

---

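### The 20-minute minimum latency is a condition of the two capsule-negative cells only, and 4.1, 10.3 and 10.4.2 disagree on whether an early-scoped capsule-negative patient is counted

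*Combined protocol and SAP*

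**What the plan says.** The synopsis (Statistical Analysis) and section 4.1 define the four cells in the same way. To score a patient as a true positive, the text asks only for this: "HemoPill acute measurement indicates presence of blood; Endoscopy identifies fresh blood or hematin in the GI lumen". The false-positive cell has the same form, with nothing seen at endoscopy, and it too is silent on latency. The two capsule-negative cells ask for more. For the true negative, the endoscopy part reads "Endoscopy does not identify fresh blood or hematin in the GI lumen in quantities > 20 mL; Minimum latency of 20 minutes achieved". The counterpart for a missed bleed reads "Endoscopy identifies fresh blood or hematin in the GI lumen in quantities > 20 mL; Minimum latency of 20 minutes achieved".

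The latency clause is thus in the last two cells only. The procedure itself has a two-sided window. Section 4.1 says "After a latency of minimum 20 minutes, maximum 60 minutes, endoscopy is performed as scheduled", and 6.3.1 says "No more than 60 minutes between HemoPill acute ingestion and start of endoscopy should elapse". The upper limit is in no cell definition.

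The primary endpoint (4.2.1) refers to the 4.1 definitions. Section 10.4.2 restates the four cells by capsule and endoscopy result alone, without latency, and then points to 4.1 for detail. It removes a patient only when one of the two results is missing. Section 10.3 says that "only patient withdrawal or termination by the investigator can lead to exclusion from the analysis dataset". Accuracy in 10.4.2 is (TP + TN) divided by a quantity called pop, which is not defined. Section 10.1 states that there is no separate SAP.

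**The concern.** Under 4.1, whether an early-scoped patient enters the table depends on the result of the test being evaluated. Early misses have no cell, but early hits do. Early correct negatives have no cell, but early false alarms do. Under 10.3 and 10.4.2, all of these patients are counted. Two analysts could build different 2 x 2 tables from the same data, and both could cite the protocol.

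The trial exists to establish accuracy parameters (2.4.1), and 2.1.1 presents its advance over earlier work as being made "by controlling and limiting latency to endoscopy". Early endoscopy is possible under the design. Endoscopy may not be delayed for the trial (2.1.1, 2.3), its timing follows urgency (5.4, 6.1.5), the capsule is given as late as possible (4.1), and compliance assessment is marked not applicable (6.3.3). The rule for such patients should be fixed before results are seen. The 20 mL cut-off is a separate matter and is left aside here.

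**Working it through.** **The plan's own figures.** Section 10.5 assumes accuracy 75%, sensitivity 100% and specificity 63%. These follow from the multicentre series in 2.1 if its 60 patients are taken as TP 20, FP 15, FN 0, TN 25: accuracy 45/60 = 75%, sensitivity 20/20 = 100%, specificity 25/40 = 62.5%, prevalence 20/60 = 1/3.

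**Direction.** Write *on* for patients scoped at 20 minutes or later and *early* for those scoped before. Under 4.1:

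- sensitivity = (TP_on + TP_early) / (TP_on + TP_early + FN_on)
- specificity = TN_on / (TN_on + FP_on + FP_early)

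Counting every early patient adds FN_early to the sensitivity denominator. Excluding every early patient removes TP_early from numerator and denominator. Neither change can raise sensitivity, so the 4.1 value is never below either symmetric rule. The mirror argument shows that specificity under 4.1 is never above either.

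A small invented example: on-time TP 10, FN 2; early TP 2, FN 1.

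- All counted: 12/15 = 80.0%
- All early excluded: 10/12 = 83.3%
- 4.1 as worded: 12/14 = 85.7%

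**Size.** The documents do not give the share s scoped early. Assume s = 5% to 30%, unrelated to disease status, with the same capsule performance in early patients. Take prevalence p = 1/3 and specificity sp = 62.5% from the series above, and true sensitivity se = 80% or 90% as assumptions. Then:

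- sensitivity = se / [se + (1 − se)(1 − s)]
- specificity = sp(1 − s) / [sp(1 − s) + 1 − sp]
- accuracy over filled cells = [p·se + (1 − p)·sp·(1 − s)] / [1 − s·(p(1 − se) + (1 − p)·sp)]

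For example, at se = 80% and s = 20%, sensitivity is 0.80 / (0.80 + 0.20 × 0.80) = 0.80/0.96 = 83.3%. Specificity is 0.50 / (0.50 + 0.375) = 57.1%.

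| s | Sensitivity (true 80%) | Sensitivity (true 90%) | Specificity (true 62.5%) | Accuracy (se 80%, true 68.3%) | Accuracy (se 90%, true 71.7%) |
|---|---|---|---|---|---|
| 5% | 80.8% | 90.5% | 61.3% | 67.9% | 71.2% |
| 10% | 81.6% | 90.9% | 60.0% | 67.4% | 70.7% |
| 20% | 83.3% | 91.8% | 57.1% | 66.4% | 69.6% |
| 30% | 85.1% | 92.8% | 53.8% | 65.3% | 68.4% |

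At se = 100%, the plan's assumption, sensitivity stays at 100% for every s. At s = 0 nothing changes.

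**The undefined denominator.** Use the prior cells 20/15/0/25 and let 20% of the 25 capsule-negative patients (5) lose their cell. TN becomes 20. If pop is the sum of the filled cells, accuracy is 40/55 = 72.7%. If pop is the 10.3 dataset, it is 40/60 = 66.7%. If 10.4.2 is followed and the 5 are counted, it stays 45/60 = 75%.

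**The case against.** The best reply is that no exclusion is planned. Section 10.4.2 gives four exhaustive cells without latency, and 10.3 keeps everyone with both results. On that reading an early miss is simply a false negative. This stands in part: the loss of these patients is one side of a conflict, not a settled rule, and a reader who infers that the plan deliberately discards early misses goes too far. It does not dispose of the point, because 4.2.1 and 10.4.2 both send the analyst to 4.1. Nor does the reference in 10.3 to full protocol participation settle it, since 10.3 explains that phrase as having both results.

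A second reply is that early endoscopy may be rare. Section 4.1 states the window without qualification, ingestion is timed around a known schedule, outpatients are recruited, and breaches are deviations under 14.3. This stands: the frequency is unknown, and the effect is nil if the minimum is always met.

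Three stronger inferences are tempting but unsupported.

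- *The primary test becomes easier to pass.* The only formal hypothesis (10.2) concerns accuracy, which falls in every scenario above where s exceeds zero. It falls whenever the capsule-negative patients removed are classified correctly more often than patients overall.
- *Early capsules miss many more bleeds, so the distortion is large.* The documents give no figure for this. The feasibility study in 2.2.5 used readings from the first 10 minutes and reported sensitivity 100% (95% CI 54 to 100%) above 20 mL. That is a small sample, but it gives no sign of a large early deficit.
- *The missing 60-minute limit adds to the inflation.* It is absent from all four cells alike, so it does not select on the capsule result.

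One might also argue that an early positive is a sound detection even if an early negative is inconclusive. Making inclusion depend on the capsule result still biases both indices. Moreover, the reason 4.1 gives for the minimum, interference from insufflation or endoscopic light, is not confined to negative readings.

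**Conclusion.** The point holds as an internal conflict in the definition of the primary endpoint. Sections 4.1, 10.3 and 10.4.2 give different answers for a capsule-negative patient scoped before 20 minutes, and the accuracy denominator is undefined. If 4.1 is followed, the direction is certain: sensitivity up, specificity down. The size rests on the assumed 5–30% scoped early and on equal early performance. Sensitivity then rises by 0.5 points (90.0% to 90.5%) up to 5.1 points (80.0% to 85.1%), and specificity falls by 1.2 to 8.7 points from 62.5%. Accuracy falls by about 0.4 to 3.3 points at true sensitivity 80–90%. What is at risk is the reported sensitivity and specificity, not a falsely positive primary test. The sample size calculation is unaffected. The silence on patients beyond 60 minutes is a separate gap.

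**What to change.** Apply one latency rule to all four cells, whatever the capsule result, and state it in the same words in the synopsis, 4.1, 10.3 and 10.4.2. Define pop as the sum of the four cells. Two symmetric rules remove the bias:

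- **All patients:** delete the latency clause from the true-negative and false-negative definitions, and classify everyone with both results.
- **In-window patients:** restrict all four cells to the window already in 4.1, and add that exclusion to 10.3.

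Name one as primary and report the other as a sensitivity analysis. Give the number of patients below 20 and beyond 60 minutes, by capsule and endoscopy result. The same rule should say how patients beyond 60 minutes are handled.

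The cost is wording in four places and one extra table. Ingestion time and endoscopy start time must both be recorded; 10.4.9.1 already plans a listing of results with time points.

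The choice has a price. With all patients as primary, the main table includes endoscopies outside the window that the protocol set. With in-window patients as primary, out-of-window patients of either capsule result leave the table and compete with dropouts for the 7 spare places in 10.5. If 10% of 50 are out of window, 45 remain, which leaves 2 places for dropout before the number falls below 43. At 20% and 30%, 40 and 35 remain, already below 43.
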